## 1.5 Measures

Assessments will be conducted at baseline, 3, 6, and 12 months. The measures below will be administered by an assessor blinded to group assignment. Participants will receive \$25 for completing the 3-month assessment and \$50 for completing the 6 and 12-month assessments.

**1.5.1 Primary Outcomes.**—Weight will be measured to the nearest 0.1 kg using a digital scale; height will be measured to the nearest millimeter with a stadiometer using standard procedures. Measurements will be made in light indoor clothing without shoes. Percent weight loss will be calculated as:  $[(\text{baseline weight} - \text{follow-up weight}) \div \text{baseline weight}] \times 100$ .

## 1.6 Statistical Analysis Plan

**1.6.1 Analytic plan.** Statistical analysis will follow good practices for the evaluation of randomized controlled trials as embodied in the CONSORT statement. Missing data will be imputed using a multiple imputation approach and outcome models averaged across imputations to adhere to the intent-to-treat principle. We will compare the sensitivity of the findings to alternative methods for handling missing data (see Missing Data Section below).

As a preliminary step, demographics, baseline weight and health history will be summarized across the aggregate sample and compared between cells (intervention components) using Analysis of Variance (ANOVA) for continuous variables, chi-squared analyses for categorical variables and non-parametric tests as appropriate. Variables will be considered potential confounders in the subsequent models if these variables are correlated with the outcome under consideration (at a modest  $p < .30$  level). The distribution of each of study outcome will be assessed using both parametric and graphical methods and transformed as necessary (e.g. log transform towards normality). Potential distributions for the outcome variables

include normal and binomial, and zero-inflated distributions.

Evaluation of the intervention components will involve generalized linear models that regress percent weight change from baseline (e.g., normal distribution & identity link function) and achievement of a  $\geq 5\%$  weight loss (binomial distribution & logit link function) on effect-coded indicators for each of the five intervention components and unique 2 through 5-way interactions of components. Effect coding  $(-1,1)$  is essential in analyzing factorial designs and results in regression weights that correspond to main effects and interactions.

Effect-coded main effects and interactions are orthogonal to one another, yielding unbiased estimation of standard errors, and equal power for main effects and interactions for given effect sizes. Using this approach, individual cell sizes (for each combination of components) does not limit statistical power. Models will adjust for confounders identified during preliminary analyses, including demographics, health and weight history that are associated with weight loss outcomes.

**1.6.2 Missing data.** Analyses will be conducted on the intent-to-treat sample (everyone randomized will be included in the final analysis) under various assumptions about the missing data mechanism. Sensitivity to these assumptions will be tested. Specifically, we will gather follow-up information and reasons for dropout regardless of protocol completion and censor at the point of loss. We will compare the robustness of our findings using three statistical approaches for handling missing data. First, we will use a multiple imputation approach to impute missing outcomes. Next, we will use inverse probability weighting with propensity scores. This is a two-step method: 1) using logistic regression, the probability of missingness is modeled as a function of baseline covariates and baseline values of the outcome and 2) the inverse of the propensity scores (predicted probabilities of dropout from the first step) serve as weights in our regression model of the outcomes. Provided the data are missing at random (MAR) or that the probability of missingness can be fully explained by observable data, this approach produces asymptotically unbiased estimates. To allow for the possibility that the MAR assumption may not hold, we will also use a third approach, pattern mixture models, in which the distribution of the outcome is assumed to follow a mixture of two distributions: one for those who complete follow up and another for those who do not.

**1.6.3 Sample size and power estimates.** Following the full factorial design, each of the planned 384 participants is randomly assigned to each of the five intervention components. There are 32 possible combinations of intervention components, but each component will be administered to 192 persons and withheld from 192 persons. Using the generic approach described by Lehr, a sample size of  $n = 192$  per group permits the detection of standardized effect sizes (SEs) of  $\Delta = (4/n^{.5})$  (where 4 encompasses standard assumptions of a type-I and type-II error rate of  $\alpha = .05$  and  $\beta = 20\%$ , respectively where  $4 \approx \sqrt{2} \times (|z\alpha/2 + z\beta|)$ , and solves to  $SE = 0.29$ ). According to estimates based on our preliminary data, RxWL without additional intervention components produces  $\geq 5\%$  weight loss for 50% of the sample, and the standard deviation on percent weight change will be 5.8% at 12-months. This generic approach estimates power to detect intervention component effects of 9% on proportion achieving  $\geq 5\%$  weight loss and effects of 1.7% on mean weight loss. Statistical power was further evaluated using Monte Carlo estimation, the model specification (with effect coding) for the proposed study, and parameter estimates based on previous RxWL trials. This tailored approach yielded estimates of 91% power to detect a component marginal effect size of  $ES = 0.16$  or an additional 3% achieving  $\geq 5\%$  weight loss and just under 1% additional weight loss due to component effects. The study is adequately powered because a lesser effect would not be clinically significant.

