**1.4.2 Participant recruitment and enrollment.** Participants will be recruited via advertisements in local media (e.g. newspapers, radio); targeted online advertising (e.g., Facebook, Google AdWords); flyers and advertisements posted in waiting rooms and exam rooms in primary care offices used in previous studies of RxWL; informational materials made available as part of the health and wellness program for employees in the Lifespan Heath System and hospital network (an approach used in a previous RxWL trial); and direct mailings. A screener completed online or by phone will be used to determine initial eligibility. Individuals who appear eligible will be invited to attend an orientation session at the research center. The study will be described in detail and participants will have the opportunity to complete informed consent, begin the baseline assessment, and schedule their randomization visit. Participants are required to complete the baseline assessment, including wearing the physical activity monitor and completing dietary recalls (described below), to be eligible for randomization.

**1.4.3 Randomization.** Prior to enrollment, a randomization schedule will be prepared based on 12 blocks of 32 patterns of assignment to each of the five intervention components. A sequentially-numbered sealed envelope containing the assignment will be opened by research staff at the time of randomization. The participant will receive brief written materials explaining their assignment and how to begin treatment via the online system. Further orientation to the treatment system is conducted online via interactive video lesson. Study staff will be available by phone to trouble-shoot technical difficulties, but no human-delivered weight loss counseling will be provided in-person or by phone. Participants will be enrolled until the total N=384 target enrollment has been satisfied.

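### The covariates in the primary models are chosen from the trial's own outcome data at p<.30 and from an open candidate list, so the models cannot be fixed before outcomes are seen

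*Combined protocol and SAP*

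**What the plan says.** Section 1.6.1 (Analytic plan) begins with a descriptive step in which "demographics, baseline weight and health history will be summarized across the aggregate sample and compared between cells". The rule for adjustment does not use that comparison between cells. It uses association with the outcome: "Variables will be considered potential confounders in the subsequent models if these variables are correlated with the outcome under consideration", with a threshold of p<.30. The section closes with "Models will adjust for confounders identified during preliminary analyses, including demographics, health and weight history that are associated with weight loss outcomes".

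There are two primary models. "Evaluation of the intervention components will involve generalized linear models that regress percent weight change from baseline" introduces the first, with a normal distribution and identity link as the example. The second is a logistic model for reaching ≥5% loss. Both contain the five effect-coded components and all their interactions.

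The plan leaves the following open:
- the list and number of candidate variables
- whether a variable that is only considered must then be entered
- whether any covariate is always included
- whether the screen runs on observed or imputed outcomes
- whether the two models share one set
- whether an unadjusted result is reported

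**The concern.** The components are randomized in 12 blocks of 32 assignment patterns (section 1.4.3), so there is no systematic confounding to remove. Adjustment serves precision, and a list fixed in advance serves that purpose. A screen on the outcome instead leaves the primary model undetermined until follow-up is complete. With an open candidate list, the result also depends on which variables the analyst chooses to screen.

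The trial exists to decide which components go into the optimized package (section 1.1). A component near the significance boundary can move across it when the covariates change. The screen is tied to each outcome separately, so the two results that are read together may come from differently adjusted models. In a logistic model, the component odds ratio is also conditional on the prognostic covariates that are included.

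**Working it through.** **Inputs from the documents.** N = 384 (section 1.4.3); 192 participants with and 192 without each component, SD of percent weight change 5.8, 50% reaching ≥5% loss, two-sided alpha .05 (section 1.6.3); threshold p<.30 (section 1.6.1).

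**Assumptions.** The documents give no number of candidates, so 5, 10 and 20 are used. Where real predictors are needed, three of the candidates together explain 10% of the outcome variance.

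**1. The plan's own figure.** 4/√192 = 0.289, and 0.289 × 5.8 = 1.67, which agrees with the stated 0.29 and 1.7%. Power at 1.7 points without adjustment: 1.7 / (5.8 × √(2/192)) = 2.87, and Φ(2.87 − 1.96) = 0.82.

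**2. How low the bar is.** With 382 degrees of freedom, p<.30 needs t of about 1.04, so |r| ≥ 1.04/√(382 + 1.04²) ≈ 0.053.

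**3. Irrelevant variables admitted.** The expected number is 0.30 × K, and P(at least one) = 1 − 0.70^K.

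| Candidates, all irrelevant | Expected to enter | P(at least one) |
|---|---|---|
| 5 | 1.5 | 83% |
| 10 | 3.0 | 97% |
| 20 | 6.0 | 99.9% |

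**4. Real predictors lost.** By Fisher's z, a predictor with r = 0.10 has mean 0.1003 × √381 = 1.96 against a cut-off of 1.04, so it is dropped in about 18% of trials. One that explains 5% of variance (r = 0.22) is dropped in about 0.03%.

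**5. Do the two models get the same set?** A normal outcome and its 50% split correlate at 0.399/0.5 = 0.798. With that correlation, an irrelevant candidate passes both screens with probability 0.182. It therefore passes exactly one with probability 2 × (0.30 − 0.182) ≈ 0.24. P(sets differ) = 1 − (1 − 0.236)^K, which is 74%, 93% and 99.5% for 5, 10 and 20 irrelevant candidates. In simulations with three real predictors among the candidates, the sets differed in 86% to 88% of trials with 10 candidates and in 99% with 20.

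**6. Error rate and power in the linear model.** Simulation with N = 384, all 32 effect-coded terms and 4,000 trials per scenario:

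| Candidates | Power at 1.7 points, p<.30 screen | Power at 1.7 points, the three real covariates fixed |
|---|---|---|
| 10 | 0.853 | 0.857 |
| 20 | 0.836 | 0.848 |

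Type I error was 0.046 to 0.056 with the screen and 0.049 to 0.056 with the fixed set (Monte Carlo SE about 0.0034).

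**7. Individual decisions.** In separate simulations all five components had a true effect of 1.7 points. Each trial was analysed with the screen and with the fixed set. At least one of the five p<.05 verdicts differed in about 10% of trials with 10 candidates and about 17% with 20. This measures how far the decision depends on the covariate set. It does not show that the screen is wrong more often.

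**The case against.** The strongest reply is that the rule is numeric, is disclosed in advance and looks at covariate–outcome correlation, not at component effects. Much of this reply stands. Strong predictors are almost never dropped, and the error rate in the linear model is nominal. In the saturated logistic model, simulated type I error was 5.6% with 15 irrelevant candidates screened, 6.5% with 30, and 6.1% with three fixed covariates (Monte Carlo SE 0.2 points). Most of that excess comes from the saturated model, and a fixed list does not remove it. The closing sentence of section 1.6.1 speaks of outcomes in the plural and could be read as one common set, so different sets are very likely but not certain.

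A reader might infer more than the documents support:
- **A large power gain.** Covariates explaining 5–20% of variance would raise power from 81% to 83–89%, but only against no adjustment. The plan does adjust, and against its own screen the gain is about 0 to 1 point.
- **Different quantities in the linear model or across missing-data methods.** With randomized components, the effect on mean percent weight change is the same quantity whichever baseline covariates enter. Section 1.6.2 does not say that selection is repeated for each missing-data method.
- **An undefined log of percent weight loss.** The plan allows outcomes to be "transformed as necessary (e.g. log transform towards normality") as a general example. It does not assign a log to percent weight change, for which it names a normal distribution and identity link.

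The reply does not answer the open candidate list or the dependence of the primary models on outcome data.

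**Conclusion.** The point holds as one of pre-specification and reproducibility. It does not show bias or inflated error. As written, the primary models cannot be fixed before outcomes are seen, and the two models very likely carry different covariates (about 88% of simulated trials with 10 candidates, 99% with 20). The choice of set can change which components are declared effective, in about 10% to 17% of simulated trials at 1.7 points. For the logistic model, the target of the odds ratio depends on which real predictors enter. Pure-noise covariates do not change it. The size of any such shift was not estimated, and neither was logistic power.

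These sizes rest on the assumed candidate counts, three real predictors explaining 10% of variance, complete data and independent normal covariates. The qualitative conclusion follows from the wording of section 1.6.1 alone. The change should be made, but the trial's validity does not hang on it.

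**What to change.** Replace the p<.30 rule, and the sentence that "Models will adjust for confounders identified during preliminary analyses", with one fixed baseline list named before outcome data are seen. Use it in both primary models and in all missing-data analyses, whatever the p-values. A workable list is baseline weight, age and sex (if sex is collected among the demographics), plus any weight-history items the sponsor names now. Report the unadjusted result as a sensitivity analysis.

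The cost is about two sentences in the SAP. Sample size does not change, and the simulations show no loss of power when the list contains the real predictors. Baseline weight is already measured, and age is already needed for eligibility. The downside is that a prognostic variable left off the list is not adjusted for, so the sponsor should choose the list with care.

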## 1. Study Protocol

### 1.1 Study aims and design

This study, sponsored by the National Institute of Diabetes and Digestive and Kidney Diseases (NIDDK), aims to optimize online behavioral lifestyle intervention (BLI) by testing whether any of five theory-driven experimental intervention components increase the proportion of individuals achieving a minimum clinically significant weight loss of  $\geq 5\%$  of initial body weight and/or mean weight loss after 12 months of treatment. The rationale and design of the study methods are informed by the 3-Phase Multiphase Optimization Strategy (MOST) framework. Per the MOST Optimization Phase, a factorial experiment will be conducted to determine which, if any, of the experimental intervention components contributes to improved treatment outcomes. Adults with a body mass index (BMI) in the overweight or moderately obese range ( $25-30 \text{ kg/m}^2$ ) will receive the preexisting 12-month Rx Weight Loss (RxWL) and a random combination of 0-5 of the experimental intervention components. A priori optimization criteria will be used to evaluate which, if any, of the experimental intervention components should be included in an optimized RxWL treatment package, which can then be tested in a future randomized controlled trial per the MOST Evaluation Phase. Mediation analysis will also be conducted to determine whether the experimental intervention components exerted their intended effects on their putative behavioral and psychosocial mechanisms, and whether those effects were associated with improved weight loss outcomes. Moderators analysis will explore for whom and under what circumstances the experimental intervention components might have been more or less effective. Assessments of weight and hypothesized mediators will occur at baseline and 3, 6, and 12 months after randomization. The study aims are:

**1.1.1 Aim 1:** Optimize RxWL via a factorial experiment to determine which combination of intervention components maximizes the proportion of participants achieving a  $\geq 5\%$  weight loss and mean weight loss at 12-months.

**1.1.2 Aim 2:** Conduct mediation analysis using proximal outcomes to test hypothesized mechanisms of action and moderator analysis to understand for whom and under what circumstances the interventions are effective.

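### With (-1,1) coding each component weight is half the on-minus-off effect, the plan states no conversion, and the 0.16 effect size in 1.6.3 appears to mix the two scales

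*Combined protocol and SAP*

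**What the plan says.** Section 1.6.1 regresses percent weight change ("normal distribution & identity link function") and achievement of ≥5% loss ("binomial distribution & logit link function") on (-1,1) indicators for the five components and all their interactions. It justifies the coding by saying that it "results in regression weights that correspond to main effects and interactions". It gives no multiplier, no back-transformation from the logit scale and no reporting scale.

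The rest of the plan speaks in on-versus-off terms. Aim 1 (1.1.1) is to "determine which combination of intervention components maximizes the proportion of participants achieving" ≥5% loss, together with mean loss. Section 1.6.3 says that "each component will be administered to 192 persons and withheld from 192 persons". It gives generic detectable effects of 1.7% in mean loss and 9% in the proportion. It then reports a Monte Carlo evaluation of the effect-coded model: 91% power at an effect size of 0.16, put into words as 3% more participants reaching the target and slightly less than 1% further weight loss. It concludes: "The study is adequately powered because a lesser effect would not be clinically significant".

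Section 1.1 says that components will be selected by optimization criteria set in advance, but gives neither a value nor a scale for them.

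**The concern.** Under (-1,1) coding, going from off to on moves the indicator by two units. A weight is therefore the change per one unit, half of what a reader understands by the effect of a component. If weights are taken as effects, every component effect and its interval appears at half size, beside planning figures that are full size.

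For the ≥5% outcome there is a second gap. The weight is half a log odds ratio, averaged over the 16 combinations of the other components and conditional on the chosen covariates. Aim 1 asks about a proportion, and the plan names no step that produces a difference in proportions.

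The purpose of the study is to judge which components are worth keeping, so the scale of the reported effects, and of the figure called the limit of clinical significance, should be beyond doubt.

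**Working it through.** **Inputs.** N = 384 in 12 blocks of 32 patterns (1.4.3), so 192 on and 192 off per component; SD 5.8 ("the standard deviation on percent weight change will be 5.8% at 12-months"); base rate 50%; two-sided α = 0.05 and 80% power for the generic calculation (all 1.6.3).

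**1. The plan's generic figure reproduces as an on-minus-off effect.** 4/√192 = 0.289 SD, and 0.289 × 5.8 = 1.67, the stated 1.7. By the normal approximation, power = Φ(d√(n/2) − 1.96). With d = 1.7/5.8 = 0.293 and √96 = 9.80, this is Φ(0.91) = 0.82.

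**2. The weight for that effect, linear model.** The prediction at +1 minus the prediction at −1, averaged over the other components, is 2b. So b = 1.7/2 = 0.85. Solving the full 32-cell model exactly gives 0.85; 4,000 simulated trials with N = 384 give a mean weight of 0.856 and power 0.818.

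| Reported quantity | Estimate | SE | 95% CI |
|---|---|---|---|
| b | 0.85 | 5.8/√384 = 0.296 | 0.27 to 1.43 |
| 2b | 1.70 | 0.592 | 0.54 to 2.86 |

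The ratio of estimate to SE is the same in both rows. In one simulated main-effects fit, the t statistic was 2.670 under (-1,1), (0,1) and (-0.5,+0.5) coding alike.

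**3. Logistic model, using the plan's 9 points.** For 50% versus 59%, the odds ratio is 0.59/0.41 = 1.44 and its log is 0.364. The weight is 0.364/2 = 0.182, and exp(0.182) = 1.20. Read as an odds ratio from a 50% base, 1.20 gives 1.20/2.20 = 54.5%: 4.5 points instead of 9.

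**4. Interactions.** The factor differs. A two-way difference of differences of 1.7 gives a weight of 0.425, so the multiplier is 4.

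**5. The scale of the 0.16.** In weight units, 0.16 × 5.8 = 0.93, which matches the plan's wording. The power under each reading is:

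| Reading of 0.16 | On-minus-off effect | Power |
|---|---|---|
| On-minus-off effect | 0.16 SD = 0.93 points | Φ(1.568 − 1.960) = 34.7% (simulated 34.8%; one-sided 46.9%) |
| Raw (-1,1) weight | 0.32 SD = 1.86 points | Φ(3.135 − 1.960) = 88.0% (simulated 88.1%) |
| Raw weight, covariates explain 10% of variance (assumed) | 0.32 SD = 1.86 points | 91.1% (89.6% to 92.5% for 5% to 15%) |

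The on-minus-off effect needed for 91% power is (1.960 + 1.341)/9.80 = 0.337 SD, half of which is 0.168. To reach 91% with 0.16 as an on-minus-off effect, covariates would have to explain 1 − (0.16/0.337)² ≈ 77% of the variance.

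**The case against.** The best reply is that the sentence in 1.6.1 is defensible. It explains why effect coding was chosen, and the weights do correspond to main effects up to a fixed constant. The plan never says that raw weights will be reported or compared with a threshold, and an experienced analyst would rescale them. This stands: half-size reporting is a risk from an unstated step, not something the plan prescribes. Averaging over the other components and conditioning on covariates are ordinary features of a factorial logistic model and not faults.

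A reader might go further and infer that a worthwhile component will be dropped, because 0.85 lies below 0.93. The documents do not support that. The optimization criteria have no stated metric, and the closing sentence of 1.6.3 defends the power rather than setting a selection rule. The example also depends on what 0.93 is. If it is an on-minus-off effect, 0.85 is being set against the wrong scale. If it is a raw weight, the limit is 1.86 points on-minus-off, and a true 1.7 does fall below it.

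Nor may one infer biased estimates or weaker tests: the t statistics do not depend on the coding.

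Finally, the reading of 0.16 as a raw weight cannot be proved. The simulation inputs are not given, and the plan's own description of additional weight loss points to an on-minus-off effect.

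**Conclusion.** The point holds as a gap in the analysis plan with a fixed size. Each main-effect weight and its interval is half the on-minus-off quantity, and no section converts it to the units of Aim 1 and 1.6.3. This follows from the coding alone and needs no assumption; the figures 0.85 and 1.20 use the plan's own SD, base rate and detectable effects. The 9 points serve only as an illustration here; whether the study has power for them is a separate matter.

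That 1.6.3 already mixes the scales is likely but inferred. Of the two readings, only the raw weight comes near 91% power without covariates that explain about three quarters of the variance. If that reading is right, the effect detectable with about 91% power is about 1.9 points rather than slightly under 1, and the limit of clinical significance is misstated by the same factor. It is worth correcting before analysis, because the remedy is specific and changes no test.

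**What to change.** In 1.6.1, after the sentence on effect coding, state that:

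- each main-effect weight is half the on-minus-off effect, and effects on percent weight loss are reported as 2b with its 95% CI (or code main effects −0.5/+0.5);
- effects on ≥5% loss are reported as the model-standardized difference in proportions, that is, the mean over all randomized participants of the predicted probability with the component on minus off, with its CI; any odds ratio is exp(2b);
- the multiplier for interactions is given (4b for a two-way difference of differences);
- clinical and optimization thresholds apply to these on-minus-off quantities.

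In 1.6.3, say whether 0.16 is a raw weight or an on-minus-off effect, give the simulation inputs, and restate the equivalent weight loss to match.

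The cost is one paragraph and a few lines of post-estimation code, with no new data and no changed test. The stated detectable effect may become less favourable.

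### The inverse probability weighting check is called unbiased under MAR, but its missingness model holds only baseline data, so dropout that follows observed 3- or 6-month weight is largely uncorrected

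*Combined protocol and SAP*

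**What the plan says.** Section 1.6.2 (Missing data) promises a sensitivity comparison: "We will compare the robustness of our findings using three statistical approaches for handling missing data". The three are multiple imputation, IPW and pattern mixture models. Section 1.6.1 shows that multiple imputation is the main handling: "Missing data will be imputed using a multiple imputation approach and outcome models averaged across imputations to adhere to the intent-to-treat principle".

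For step 1 of IPW, section 1.6.2 states that "the probability of missingness is modeled as a function of baseline covariates and baseline values of the outcome". It names neither an interim weight nor the component assignment. The claim of asymptotic unbiasedness follows, under this condition: "Provided the data are missing at random (MAR) or that the probability of missingness can be fully explained by observable data". Pattern mixture models are then offered for the case where MAR fails.

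The observed data are wider than baseline. Section 1.1 says "Assessments of weight and hypothesized mediators will occur at baseline and 3, 6, and 12 months after randomization", and section 1.5 repeats the schedule. Section 1.6.2 itself says "we will gather follow-up information and reasons for dropout regardless of protocol completion and censor at the point of loss".

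**The concern.** The condition and the model do not match. A participant who has a poor observed 6-month weight and then leaves has a dropout probability that observable data explain. That satisfies the stated condition, but the step 1 model cannot see the 6-month weight. IPW removes only the part of the selection that baseline variables predict.

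What is at stake is the value of the robustness check. If early weight loss drives dropout and baseline variables predict it poorly, this analysis nearly repeats a complete-case analysis. Its agreement or disagreement with multiple imputation could then be misread. The other two approaches do not clearly fill the gap. The imputation variables are not listed, so imputation may or may not use the interim weights. Pattern mixture is reserved for when MAR fails, and dropout explained by an observed interim weight is MAR.

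**Working it through.** **The logic needs no figures.** MAR means that missingness may depend on any observed data, here including 3- and 6-month weight. The specified model is valid under a narrower condition: missingness depends only on the baseline variables in it. No section adds interim weights to the model or narrows the claim.

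**Inputs from section 1.6.3.** SD of 12-month percent change 5.8; 50% of participants reach 5% loss without added components (control mean set to 5.0 to match); 192 participants per level of each component, N = 384. The plan's detectable effect reproduces: 4/√192 = 0.289, and 0.289 × 5.8 = 1.67, stated as 1.7. A smaller effect is 0.16 × 5.8 = 0.93, the plan's figure of just under 1%. The unbiasedness claim has no figure of its own to reproduce.

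**Assumptions, because the documents give none.** 20% dropout; 6-to-12-month correlation 0.7 to 0.83; dropout log-odds slope -1 per SD of 6-month loss; one baseline covariate correlated 0.2 with early loss. All weights are 1/P(observed), so the results do not depend on how step 2 words the weight. Simulations used one million or more participants, unless stated otherwise.

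**Control check.** If dropout depends on baseline only, baseline-only IPW recovers the effect: 1.72 against a true 1.72.

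**Dropout driven by 6-month loss, same mechanism at both levels of a component** (20% dropout, correlation 0.7):

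| Estimator | Control mean | Component mean | Effect | Control share with ≥5% loss |
|---|---|---|---|---|
| Truth | 5.00 | 6.71 | 1.71 | 49.9% |
| Complete case | 5.78 | 7.34 | 1.56 | 55.3% |
| IPW, baseline only | 5.76 | 7.31 | 1.56 | 55.2% |
| IPW, plus component and 6-month loss | 5.00 | 6.71 | 1.71 | 49.9% |

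The control mean is shifted by 5.76 - 5.00 = 0.76 and the component mean by 7.31 - 6.71 = 0.60. The shifts largely cancel in the contrast, leaving attenuation of about 0.16 (0.15 from the rounded effects). With a zero effect they cancel fully (within 0.01).

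Over correlations of 0.7 to 0.83, the control mean is about 5.7 to 5.9, control responders are 55 to 56%, and a true 1.70 becomes about 1.5 to 1.6. The standard error of a component effect is 2 × 5.8/√(384 × 0.8) = 0.66, so a loss of 0.16 is 0.16/0.66 = 0.24 SE.

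**Same slope, dropout rates of 15% and 25%.** The shifts no longer cancel. A true zero becomes 0.32 to 0.41 in size, in the direction set by which level loses more participants; 0.32/0.66 to 0.41/0.66 is 0.48 to 0.62 SE. A true 1.70 becomes 2.00 to 2.08 or 1.34 to 1.38. Adding component and 6-month loss removes this in large samples.

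**Slope differing by component.** In the extreme case, where 6-month loss drives dropout only among those given the component, a true 1.70 becomes 2.42. Adding component assignment without interim weight leaves it at 2.39.

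**Sensitivity to the assumptions** (same mechanism at both levels):
- 10 to 30% dropout with correlation 0.5 to 0.83: control mean 5.25 to 6.26; effect 1.51 to 1.64 for a true 1.70.
- 20% dropout, correlation 0.7: slope -0.5 gives control mean about 5.4 and effect 1.67; slope -1.5 gives about 6.0 and 1.47.
- Baseline covariate correlation of 0.6 instead of 0.2: control mean about 5.5, so good baseline predictors reduce the bias.

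**The case against.** The strongest reply is that IPW is one of three approaches and not the main one. The trial's decisions rest on component contrasts rather than group means. Under a common mechanism the contrast bias is about a quarter of an SE and vanishes under the null. The sizes rest on assumed dropout, correlation and slope. On this view only a wording slip remains.

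Much of that stands. IPW is secondary and the magnitudes are illustrative. The richer model also gives no gain in root mean squared error for the effect at N = 384 (0.66 to 0.68, against 0.63 to 0.65 for baseline-only). What does not stand is that contrasts are safe in general: unequal dropout rates with a common slope are enough to create a spurious effect. The documents neither state nor exclude such a difference.

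A second reply is that MAR was meant as MAR given the model's covariates. The alternative condition, that observable data explain missingness, carries no such limit.

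Two stronger readings are tempting. A reader might infer that the primary analysis is biased. The documents do not support this, because that analysis uses multiple imputation with unlisted variables, which could include interim weights. A reader might also infer that the plan expressly promises to correct dropout driven by interim weight. It never mentions that mechanism; the overreach comes from the general condition.

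**Conclusion.** The concern holds in a limited form. The unbiasedness statement is too broad for the model specified, and this follows from the text alone. It is valid only for missingness that depends on the baseline variables in the model. Dropout driven by observed 3- or 6-month weight is largely, not wholly, uncorrected, since the part that baseline predicts is still handled.

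The size depends on the assumed mechanism. In the main scenarios group means and responder rates are too high: by about 0.7 to 0.9 percentage points of weight loss, and 5 to 6 points in control responders. The contrast is modestly attenuated if the mechanism is common to both levels. It can move in either direction if dropout rates or slopes differ by component. The plan should be corrected because the statement is wrong and the repair is cheap, not because a primary conclusion has been shown to fail.

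**What to change.** 1. **Wording (the minimum).** Limit the claim, for example: *If missingness of the 12-month weight is explained by the variables in the step 1 model, and that model is correctly specified, the weighted estimates are asymptotically unbiased.* If the model stays as it is, say that those variables are baseline only. This costs one sentence.

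2. **Model (preferable).** Add the five component indicators and the observed interim percent weight change to the step 1 logistic model. Use either the latest available value or sequential weights by visit.

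3. **Rule for gaps.** Section 1.4.2 makes baseline complete for everyone randomized ("Participants are required to complete the baseline assessment"), so only interim weights need a rule. In a simulation with 3-, 6- and 12-month visits, setting a missing interim change to zero over-corrected (control mean 4.40 to 4.57 against 5.00). Using the mean observed change gave 4.85 to 4.96, which is closer but not exact.

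The model change uses data already collected and needs little programming. In simulations at N = 384 the weights are slightly more variable: the effective sample averages about 94% of completers, against over 99% for baseline-only. A main-effects model also does not remove contrast bias when the slope itself differs by component. With a half-strength slope at one level, a true 1.70 is estimated as 1.29 to 1.34 or 1.97 to 2.06, against 1.24 to 1.32 or 1.91 to 1.98 for baseline-only. Component-by-interim-weight terms could be an optional further sensitivity analysis; with about 0.2 × 384 = 77 dropouts they should not be the default.
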